7.1.2.3.2 SDAI REMISSION

At each time point (M3, M6, M9, M12, M15, M18, M21, M24) SDAI is calculated as:

$$SDAI = TJC28 + SJC28 + PhyGA \text{ in cm} + PtGA \text{ in cm} + CRP \text{ in mg/dL}$$

$SDAI_Remission = 1$, if $SDAI \leq 3.3$
 $SDAI_Remission = 0$, otherwise.

The proportion of patients in SDAI Remission at Month X is then calculated as:

No. of patients with SDAI Remission at Month X / Total Number of patients with non-missing SDAI Remission at Month X.

7.1.2.3.3 CDAI REMISSION

At each time point (M3, M6, M9, M12, M115, M18, M21, M24) CDAI Remission is derived as:

$$CDAI = TJC28 + SJC28 + PhyGA \text{ in cm} + PtGA \text{ in cm}$$

$CDAI_Remission = 1$, if $CDAI \leq 2.8$
 $CDAI_Remission = 0$, otherwise.

The proportion of patients in CDAI Remission at Month X is then calculated as:

No. of patients with CDAI Remission at Month X / Total Number of patients with non-missing CDAI Remission at Month X.

7.1.2.3.4 DAS28-4 (ESR) REMISSION

At each time point (M3, M6, M9, M12, M115, M18, M21, M24) DAS 28-4 (ESR) Remission is derived as:

$$\begin{aligned} \text{DAS 28-4 (ESR)}_{\text{Remission}} &= 1, & \text{if DAS28-4 (ESR)} &< 2.6 \\ \text{DAS 28-4 (ESR)}_{\text{Remission}} &= 0, & \text{otherwise.} \end{aligned}$$

The proportion of patients in DAS 28-4 (ESR) Remission at Month X is then calculated as:

No. of patients with DAS 28-4 (ESR) Remission at Month X / Total Number of patients with non-missing DAS 28-4 (ESR) Remission at Month X.

7.1.2.3.5 DAS28-4 (CRP) REMISSION

At each time point (M3, M6, M9, M12, M115, M18, M21, M24) DAS 28-4 (CRP) Remission is derived as:

$$\begin{aligned} \text{DAS 28-4 (CRP)}_{\text{Remission}} &= 1, & \text{if DAS28-4 (CRP)} &< 2.6 \\ \text{DAS 28-4 (CRP)}_{\text{Remission}} &= 0, & \text{otherwise.} \end{aligned}$$

The proportion of patients in DAS 28-4 (CRP) Remission at Month X is then calculated as:

No. of patients with DAS 28-4 (CRP) Remission at Month X / Total Number of patients with non-missing DAS 28-4 (CRP) Remission at Month X.

7.1.2.4 CHANGE FROM BASELINE IN DAS28-4 (ESR) AND DAS28-4 (CRP)

7.1.2.4.1 DAS28-4

$\text{DAS28-4 (ESR)} = 0.56*\sqrt{(\text{TJC28})} + 0.28*\sqrt{(\text{SJC28})} + 0.70*\ln(\text{ESR in mm/ hour}) + 0.014*\text{PtGA in mm.}$

DAS28-4 (CRP) is similarly calculated by:

$\text{DAS28-4 (CRP)} = 0.56*\sqrt{(\text{TJC28})} + 0.28*\sqrt{(\text{SJC28})} + 0.36*\ln(\text{CRP in mg/l} + 1) + 0.014*\text{PtGA in mm} + 0.96$

Where TJC28 is the Tender Joint Count, SJC28 is the Swollen Joint Count, CRP is the C-reactive protein in mg/L, ESR is the Erythrocyte Sedimentation Rate in mm/first hour and

PtGA is the Patient's Global Assessment of Health in mm. PtGA will be used in this calculation.

The change from baseline in DAS28-4 (ESR) will be calculated at each time point as:

DAS28-4 (ESR) at time point – DAS28-4 (ESR) at baseline.

Similarly change from baseline in DAS28-4 (CRP) will be calculated at each time point as:

DAS28-4 (CRP) at time point – DAS28-4 (CRP) at baseline.

Change from Baseline in DAS 28-4 at all time points (M3, M6, M9, M12, M15, M18, M21, M24) will be presented.

7.1.2.5 CHANGE FROM BASELINE IN DURATION OF MORNING STIFFNESS

The duration of stiffness in the morning will be provided in the eCRF.

The change from baseline in duration of morning stiffness will be calculated as.

Morning Stiffness at time point – Morning Stiffness at baseline.

7.1.2.6 CHANGE FROM BASELINE IN FFBH

The FFBH questionnaire consists of 18 questions with 3 possible responses (Yes; Yes, but with effort; No or only with outside help).

The total score is the sum of the scores of all 18 questions, where for each question:

- Yes = 2 points
- Yes, but with effort = 1 point
- No or only with outside help = 0 points

The Functional capacity [%] is then

(Total score*100)/(2*number of valid responses)

The change from baseline will then be calculated at each time point as:

Functional capacity at timepoint – Functional capacity at baseline

Change from Baseline in FFBH functional capacity at all time points (M3, M6, M9, M12, M15, M18, M21, M24) will be presented.

7.1.2.7 RATE OF FUNCTIONAL REMISSION (FFBH)

At each time point FFbH remission is derived as:

$$\text{FFbH_Remission} = 1, \quad \text{if FFbH} > 83\%$$

$$\text{FFbH_Remission} = 0, \quad \text{Otherwise}$$

The proportion of patients with FFbH Functional Remission at Month X is then calculated as:

No. of patients with FFbH_Remission at Month X / Total Number of patients with non-missing FFbH Remission at Month X.

7.1.2.8 CHANGE FROM BASELINE IN EQ-5D

The EQ-5D is a self-reported questionnaire developed by the European Quality of Life (EuroQoL) Group. It is a standardised instrument used to measure quality of life. Change from baseline in EQ-5D will be collected over time and analysed for patients taking tofacitinib. It is based on five dimensions: mobility, self-care, usual activities, pain/discomfort and anxiety/depression. Each dimension has three responses and the patient is asked to select the response that best describes them. The responses are scored 1-3 as shown in Table 2.

Table 2: EQ-5D scores

Dimension	Response	Score
Mobility	I have no problems in walking about	1
	I have some problems in walking about	2
	I am confined to bed	3
Self-care	I have no problems with self-care	1
	I have some problems washing or dressing myself	2
	I am unable to wash or dress myself	3
Usual activities (e.g. work, study, housework, family or leisure activities)	I have no problems with performing my usual activities	1
	I have some problems with performing my usual activities	2
	I am unable to perform my usual activities	3
Pain/discomfort	I have no pain or discomfort	1
	I have moderate pain or discomfort	2
	I have extreme pain or discomfort	3

Anxiety/depression	I am not anxious or depressed	1
	I am moderately anxious or depressed	2
	I am extremely anxious or depressed	3

The score for each dimension is weighted in accordance with **Table 3**.

Table 3: EQ-5D Weightings

Weights from Germany are used:

EQ-5D Dimension	Score = 1	Score = 2	Score = 3
Mobility	0	0.069	0.314
Self-Care	0	0.104	0.214
Usual Activities	0	0.036	0.094
Pain/Discomfort	0	0.123	0.386
Anxiety/Depression	0	0.071	0.236

The following algorithm is then applied to calculate the EQ-5D Total Score:

1. If all five EQ-5D dimensions have a score of 1 then the EQ-5D Total Score is 1.
2. If any of the five EQ-5D dimensions have a score of 3, then the EQ-5D Total Score is:

$$1 - 0.081 - (\sum_{1}^{5} \text{weighted dimension score}) - 0.269$$

3. If none of the five EQ-5D dimensions has a score of 3, then the EQ-5D Total Score is:

$$1 - 0.081 - (\sum_{1}^{5} \text{weighted dimension score})$$

Missing weighted dimension scores are replaced by the mean of the non-missing weighted dimension scores. If a weighted score is missing and replaced in this way by a mean weighted score of zero, step 3 of the algorithm is applied.

The change from baseline in EQ-5D will be calculated for each time point as:

$$\text{EQ-5D at timepoint X} - \text{EQ-5D at baseline}$$

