Change from baseline in EQ-5D score	FAS, including only data collected with patient remained on tofacitinib		Therapy Sequence, RA Medication History, Switch Status, Number of Treatment Switches (Section 6.6)	Summary Tables (Section 9.1.3)		No imputation
Change from baseline in FACIT score.	FAS, including only data collected with patient remained on tofacitinib		Therapy Sequence, RA Medication History, Switch Status, Number of Treatment Switches (Section 6.6)	Summary Tables (Section 9.1.3)		No imputation
Drug Survival	FAS			Kaplan-Meier Plots and Table (Section 9.1.2)		No imputation
Patient's Satisfaction with Drug Treatment	FAS,		Therapy Sequence, RA Medication History, Switch Status, Number of Treatment Switches	Summary Tables (Section 9.1.5)		No imputation

			(Section 6.6)			
--	--	--	------------------	--	--	--

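### The EQ-5D-3L rule fills a missing dimension with the mean of the other dimensions' weights, which are on different scales, and so produces index values that the blank item could not have given

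*SAP*

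**What the plan says.** SAP 7.1.2.8 scores the five EQ-5D-3L dimensions with the weights in its Table 3. A patient at level 1 throughout scores 1. Otherwise the index is 1 minus 0.081 minus the sum of the weights, with a further 0.269 subtracted if any dimension is at level 3.

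For incomplete questionnaires it adds: "Missing weighted dimension scores are replaced by the mean of the non-missing weighted dimension scores". It then covers the case where all answered dimensions are at level 1: "If a weighted score is missing and replaced in this way by a mean weighted score of zero, step 3 of the algorithm is applied". Protocol 7.9.2.2.6 carries the same two sentences. Neither document limits the inserted value to the missing dimension's own range or requires a minimum number of answered dimensions.

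In SAP 9.2.6, the row for "Change from baseline in EQ-5D score" has an entry of no imputation in the missing-data column. SAP 8.3 says that continuous endpoints are not imputed unless another section says so. SAP 8.4 says that the questionnaires come with their own replacement rules, and that scores still missing afterwards are taken as missing at random.

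**The concern.** Averaging a patient's other item scores is reasonable when the items share a scale. Here it is applied after weighting, and the weights do not share one. Two rows of Table 3 show this: "Usual Activities 0 0.036 0.094" and "Pain/Discomfort 0 0.123 0.386". The worst possible answer on usual activities costs less than a moderate answer on pain. A mean dominated by pain or mobility is therefore too large for a blank usual-activities item, and a mean of the lighter dimensions is too small for a blank pain item.

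Change from baseline in EQ-5D is secondary endpoint (h). An index scored this way enters the visit means alongside correctly scored ones. If the blank item is at baseline, the error carries into all of that patient's change scores.

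**Working it through.** The plan gives no figure to reproduce here, so the check applies its algorithm to every answer pattern.

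**Inputs** (SAP 7.1.2.8, Table 3; weights for levels 1 / 2 / 3):

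- Mobility 0 / 0.069 / 0.314
- Self-care 0 / 0.104 / 0.214
- Usual activities 0 / 0.036 / 0.094
- Pain/discomfort 0 / 0.123 / 0.386
- Anxiety/depression 0 / 0.071 / 0.236

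Whether the 0.269 term applies is decided from the answered dimensions.

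**Attainable values.** The 243 complete health states run from 1.000 (all level 1) to 1 - 0.081 - (0.314 + 0.214 + 0.094 + 0.386 + 0.236) - 0.269 = -0.594 (all level 3). The highest value below 1.000 is 1 - 0.081 - 0.036 = 0.883.

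**One dimension missing.** There are 5 x 81 = 405 patterns. In each, the inserted weight is the sum of the four answered weights divided by 4.

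| Blank dimension | Its level-3 weight | Largest inserted weight | Patterns above level 3 |
|---|---|---|---|
| Mobility | 0.314 | 0.2325 | 0 of 81 |
| Self-care | 0.214 | 0.2575 | 4 of 81 |
| Usual activities | 0.094 | 0.2875 | 55 of 81 |
| Pain/discomfort | 0.386 | 0.2145 | 0 of 81 |
| Anxiety/depression | 0.236 | 0.252 | 2 of 81 |
| All | | | 61 of 405 |

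All 61 include at least one level-3 answer; none of the 80 patterns without one breaches the ceiling. In all 61 the index is lower than any answer to the blank item could make it.

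**Totals.**

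- 378 of 405 equal none of the attainable totals. The other 27 coincide with an unrelated state. No total equals one of the three values that the patient could truly have.
- 344 of 405 lie between the lowest and highest of those three values.
- Four fall below -0.594. The lowest has usual activities blank and the rest at level 3: the inserted weight is (0.314 + 0.214 + 0.386 + 0.236)/4 = 0.2875 and the index is 1 - 0.081 - 1.150 - 0.2875 - 0.269 = -0.7875.

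**Worked cases.**

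- Level 2 throughout, complete: 0.919 - 0.403 = 0.516.
- The same patient, usual activities blank: the inserted weight is (0.069 + 0.104 + 0.123 + 0.071)/4 = 0.09175, against a true 0.036. The index is 0.919 - 0.367 - 0.09175 = 0.460, too low by 0.056.
- The same patient, pain blank: the inserted weight is (0.069 + 0.104 + 0.036 + 0.071)/4 = 0.070, against a true 0.123. The index is 0.919 - 0.280 - 0.070 = 0.569, too high by 0.053.
- Usual activities blank, pain at level 3, the other three at level 2: the inserted weight is (0.069 + 0.104 + 0.386 + 0.071)/4 = 0.1575, against a maximum of 0.094.
- Four level-1 answers and one blank: the zero-mean sentence sends this case to step 3, giving 1 - 0.081 = 0.919. No complete questionnaire can score between 0.883 and 1.000.

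**More than one missing.** The inserted weight exceeds the ceiling of at least one blank dimension in 78 of 270 patterns with two missing, 34 of 90 with three and 6 of 15 with four. If only pain is answered, at level 3, the index is 1 - 0.081 - 5 x 0.386 - 0.269 = -1.28.

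**The case against.** **Range.** A reader might infer that every visit with a blank item gets an index outside the instrument's range. That is not so: with one item blank only 4 of 405 totals leave the range, and 344 lie between totals that the patient could have had. An imputed value that matches no health state is also not wrong in itself. The ceiling breach is almost entirely a usual-activities problem and always needs a level-3 answer elsewhere. This part of the objection stands and narrows the point. It does not rescue the rule, because the level-2 example goes wrong in both directions without any breach.

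**Contradiction.** A reader might also infer that SAP 9.2.6 flatly contradicts 7.1.2.8. The documents do not support that. SAP 8.3 allows stated exceptions and 8.4 accepts questionnaire replacement rules. SAP 9.2.3.8 omits the no-imputation sentence that the FFbH section (9.2.3.6) carries. FFbH is prorated over valid responses in 7.1.2.6, yet its row in 9.2.6 also says no imputation. The entry can therefore be read as covering wholly missing scores. But 9.2.6 does not say so, and 8.4 names the EQ-5D-5L although the 3L is used, so the wording still needs reconciling.

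**Frequency.** Protocol 7.6.14 asks site staff to check the form for completeness. Protocol 7.12 expects individual missing items, but its examples are CRP and the FFbH. Blank EQ-5D items may be rare. This stands.

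**Milder repairs.** A cap at the dimension's own maximum, or a minimum number of answered items, would lose less data. A cap would leave the level-2 example unchanged, since 0.09175 is already below 0.094. A minimum of four answered items would leave every one-missing result above unchanged.

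**Conclusion.** The replacement rule is faulty as written. It averages weights that are not comparable across dimensions. With one item blank it inserts more than the dimension's worst weight in 61 of 405 patterns, gives four totals below -0.594, and errs by about 0.05 in either direction for a patient at level 2 throughout. With no minimum number of answers, it can give an index as low as -1.28.

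The counts treat all answer patterns alike and are not patient frequencies. No item-missingness rate is given, so the effect on mean change from baseline cannot be sized, and nothing here shows that it is large. The 0.919 case costs the patient 0.081 only if the blank item was truly level 1. EQ-5D is a descriptive secondary endpoint and the primary analysis is unaffected. This is a minor point, worth correcting because the correction is easy.

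**What to change.** In SAP 7.1.2.8, delete the replacement sentence and the zero-mean sentence that depends on it. State that the EQ-5D index is missing when any dimension is missing, and that the answered dimensions are still tabulated by level. Record this as a departure from protocol 7.9.2.2.6. Protocol 7.9 lets the SAP modify the planned analyses and calls for an amendment only for major changes to primary endpoint definitions or their analyses. The entry in SAP 9.2.6 then agrees with 7.1.2.8. Correct the instrument name in 8.4 at the same time.

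The cost is small. Questionnaires with a blank item leave the index tables, though not the dimension tables. Three interim analyses covered the secondary endpoints with the same methods as the final analysis (SAP 4.1), so final EQ-5D values may differ slightly from interim ones. The study report should note this.

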7.1.2.9 CHANGE FROM BASELINE IN FACIT-FATIGUE

The FACIT-Fatigue score is derived by taking the sum of the scores for the 13 questions in the instrument, resulting in a score between 0 and 52.

The change from baseline in FACIT-Fatigue score will be calculated for each time point as:

FACIT-Fatigue score at time point X – FACIT-Fatigue score at baseline

7.1.2.10 DRUG SURVIVAL STATUS OF TOFACITINIB

For patients who terminate tofacitinib, the drug survival status will be recorded as follows:

Those who terminate tofacitinib:

- Status = 1
- Time = Termination date tofacitinib – Date of initiation on tofacitinib

Tofacitinib is terminated when indicated on instrument “Rheumatologische Medikation” for therapy class tsDMARD/bDMARD variable *Change* (BDCM.CHANGECD) is set to “Therapy stop”. Tofacitinib pauses, where variable *Change* is set to “Therapy paused”, are not considered terminations.

Patients who do not terminate tofacitinib:

- Status = 0
- Time = Date of final visit – Date of initiation on tofacitinib

If patient is lost to follow-up or withdraws from the study they will be censored at the date of their last visit.

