6.1. Endpoints

6.1.1. Primary Endpoint:

Impact of the following factors on the number of treatment escalations of Tofacitinib patients in 24 months

- a. DAS28-4 with Erythrocyte Sedimentation Rate (ESR)
- b. Δ DAS28-4 (ESR)
- c. Physician Global Assessment of Arthritis
- d. Patient's Assessment of Arthritis Pain
- e. Patient's satisfaction with drug treatment
- f. Patient's Global Assessment of Arthritis

Treatment escalation in this study is defined as a switch to another DMARD or combination of DMARDs when compared to the last visit.

6.1.2. Secondary Endpoints:

- a) Time to first treatment escalation
- b) Rate of Low Disease Activity (LDA) over time of patients on Tofacitinib (in combination therapy or monotherapy), as assessed by: Simplified Disease Activity Index (SDAI) \leq 11; Clinical Disease Activity Index (CDAI) \leq 10; DAS 28-4 (ESR) \leq 3.2 and DAS28-4 with C-reactive Protein (CRP) \leq 3.2.
- c) Rate of remission over time of patients on Tofacitinib (in combination therapy or monotherapy), as assessed by: American College of Rheumatology (ACR)-EULAR Boolean remission criteria; SDAI \leq 3.3; CDAI \leq 2.8; DAS 28-4 (ESR) $<$ 2.6 and DAS28-4 (CRP) $<$ 2.6
- d) Change from baseline over time of patients on Tofacitinib (in combination therapy or monotherapy) in DAS 28-4 (ESR) and DAS 28-4 (CRP)
- e) Change from baseline of duration of morning stiffness over time of patients on Tofacitinib (in combination therapy or monotherapy)

- f) Change from baseline in the Functional Ability Questionnaire Hannover (FFbH) over time of patients on Tofacitinib (in combination therapy or monotherapy)
- g) Rate of patients with functional remission in FFbH (FFbH > 83%) over time of patients on Tofacitinib (in combination therapy or monotherapy)
- h) Change from baseline in a self-report questionnaire (a quality of life instrument) developed by the European Quality of Life (EuroQoL) Group (EuroQoL EQ-5D) over time of patients on Tofacitinib (in combination therapy or monotherapy)
- i) Change from baseline in Functional Assessment of Chronic Illness Therapy (FACIT)-Fatigue scale over time of patients on Tofacitinib (in combination therapy or monotherapy)
- j) Drug survival at month 12, 24 of patients on Tofacitinib (in combination therapy or monotherapy)
- k) Patient's satisfaction with Tofacitinib treatment (in combination therapy or monotherapy) over time

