6.3 SECONDARY FULL ANALYSIS SET

Patients with data collected while taking tofacitinib will be assigned to the Secondary Full Analysis Set (SFAS) at a given time point, which will be used for all secondary endpoint analyses. A patient is considered on tofacitinib at a given timepoint if the patient has not terminated or paused tofacitinib at the time of the visit or event. Termination or pauses are documented in eCRF instrument “Rheumatologische Medikation” for therapy class tsDMARD/bDMARD, where variable *Change* (BDCM.CHANGECD) is set to “Therapy stop” = termination or set to “Therapy paused” = pause.

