9.2.3 SECONDARY ANALYSES

All secondary endpoints will be analysed using the SFAS.

Other subgroup analyses maybe carried out, these will be defined prior to database lock.

NOTE: Although a subject will be included in the analysis set regardless of their sequence of treatment, only data collected while a subject was on tofacitinib will be included in the secondary analyses. Methods used are described in Section 9.1.2 - 9.1.4.

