9.2.3.10 DRUG SURVIVAL STATUS OF TOFACITINIB

Time to cease taking tofacitinib (drug survival) will be analysed as per Section 9.1.2, using the SFAS. Missing data will not be imputed (as per Section 8.1).

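### SAP 7.1.2.10 has no rule for a tofacitinib pause that is never resumed, so such a patient stays at risk as on drug until the final or last visit and drug survival is overstated

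*SAP*

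**What the plan says.** Protocol 6.1.2 lists the secondary endpoint as "Drug survival at month 12, 24 of patients on Tofacitinib (in combination therapy or monotherapy" and gives no rule on pauses.

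SAP 7.1.2.10 supplies the rule. A patient is an event only when the eCRF change variable is set to the stop value, and then "Time = Termination date tofacitinib – Date of initiation on tofacitinib". Entries with the pause value "are not considered terminations". Everyone without a stop has status 0 and "Time = Date of final visit – Date of initiation on tofacitinib". For early leavers: "If patient is lost to follow-up or withdraws from the study they will be censored at the date of their last visit".

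SAP 6.3 uses the same eCRF variable to decide which data enter the Secondary Full Analysis Set (SFAS). A patient is on tofacitinib at a time point "if the patient has not terminated or paused tofacitinib at the time of the visit or event".

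SAP 9.2.3.10 states: "Time to cease taking tofacitinib (drug survival) will be analysed as per Section 9.1.2, using the SFAS". The general note in SAP 9.2.3 adds that "only data collected while a subject was on tofacitinib will be included in the secondary analyses". The summary table in SAP 9.2.6 lists the FAS for drug survival instead.

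**The concern.** Leaving out short interruptions is a common and sensible choice. The gap is that the rule sets neither a maximum length nor a resumption condition, and no other section turns an open pause into a stop. A patient who pauses for good has ceased taking the drug, yet the analysis records no event and keeps counting time on drug. For these patients the error runs one way only, towards better drug survival.

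The reported figures at months 12 and 24 are what is at stake. The month-24 survivors can include patients whose month-24 data SAP 6.3 has removed from the low disease activity, remission and change-from-baseline tables because they are off drug. A reader who compares the survival curve with those denominators would find a difference that the plan does not explain.

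**Working it through.** **No figure to reproduce.** Neither document states a drug-survival rate or a pause rate. The check applies the rule to one patient and then to a cohort with assumed rates.

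**One patient.** Days are taken from the visit-window table in SAP 12.1.1: start on day 1, pause on day 182 (the month 6 target), no resumption, no stop entry, final visit on day 730 (the month 24 target).

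- SAP 7.1.2.10: status 0, time = 730 − 1 = 729 days.
- Unresumed pause counted as a stop: status 1, time = 182 − 1 = 181 days.
- Difference: 729 − 181 = 548 days credited as on drug.

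**General size.** Ignore loss to follow-up. Let F(t) be the share of patients with a recorded stop by time t. Let q(t) be the share whose unresumed pause began by t and who never have a stop recorded.

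- Survival under the SAP rule: 1 − F(t).
- Survival with unresumed pauses as stops: 1 − F(t) − q(t).
- Overstatement: q(t).

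**With numbers.** N = 1500 is the planned size (SAP 3.1). The shares of stops (30%, 50%) and of unresumed pauses (1% to 10%) are assumptions. Stop and pause times are drawn uniformly over 24 months in one simulated draw per row, with no loss to follow-up. Each survival cell shows the SAP rule, then unresumed pauses as stops.

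| Recorded stops | Unresumed pauses | Patients | Month 12 | Month 24 |
|---|---|---|---|---|
| 30% | 1% | 15 | 84.3% → 83.7% | 70% → 69% |
| 30% | 2% | 30 | 85.3% → 84.3% | 70% → 68% |
| 30% | 5% | 75 | 85.1% → 82.5% | 70% → 65% |
| 30% | 10% | 150 | 85.3% → 80.1% | 70% → 60% |
| 50% | 1% | 15 | 73.7% → 72.9% | 50% → 49% |
| 50% | 2% | 30 | 75.8% → 74.6% | 50% → 48% |
| 50% | 5% | 75 | 75.3% → 72.9% | 50% → 45% |
| 50% | 10% | 150 | 75.5% → 71.1% | 50% → 40% |

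The month-24 fall equals the assumed share, as the formula requires. The month-12 fall is 0.6 to 5.2 points, about half as large, because only pauses begun by month 12 count.

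**Which curve would be drawn.** Under SAP 7.1.2.10 with the FAS (SAP 9.2.6), the example patient contributes 729 days without an event. A literal on-drug reading of SAP 6.3, 9.2.3 and 9.2.3.10 would end that patient's follow-up near 181 days, also without an event. Two programmers could produce different curves, and neither would record the discontinuation.

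**The case against.** **The two sections ask different questions.** A reader might infer that SAP 6.3 and 7.1.2.10 flatly contradict each other. They do not. Section 6.3 asks whether a patient is on drug at a visit, and 7.1.2.10 asks whether treatment has been terminated. A paused patient can be off drug without having terminated, and the remedy keeps that distinction for resumed pauses. This objection stands. What it leaves untouched is the pause that never ends.

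**Switches should carry a stop date.** A reader might infer that anyone moved to another agent during a pause is also scored as a survivor. Protocol 7.6.5 asks for the stop date of the previous DMARD at any escalation. Protocol 7.6.19 asks for the reason for discontinuation when a patient is switched, and SAP 7.1.1 describes a monotherapy switch as stopping one drug and adding another. Most such patients should have a stop on record, so this case is residual. A patient who pauses and starts nothing falls outside the stop-date request.

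**Sites may correct the entry.** RA treatment is to be documented at every visit, and edit checks, queries and quarterly remote calls (Protocol 7.8, 7.11) may turn an open pause into a stop. That would lower the frequency. But visits are not mandatory (Protocol 7.5.2), data cleaning is expressly limited (Protocol 7.8), and neither document requires an open pause to be updated. The eCRF was not available for this check.

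**Dating an event at pause start looks ahead.** Whether the pause counts depends on what is seen later. A patient lost soon after a pause becomes an event, while a similar patient followed longer may resume, and a brief pause still open at month 24 becomes a stop. This is a fair criticism. It is why the rule needs sensitivity runs on either side, but it does not remove the bias for pauses that are never resumed.

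**Conclusion.** The gap is real and its direction is known. A patient with an unresumed pause and no stop entry is kept at risk as on drug to the final or last visit, so time to ceasing tofacitinib is overstated by about the share of patients whose unresumed pause began before the month in question. That result ignores other censoring.

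The size cannot be taken from the documents. The 1% to 10% range is an assumption, and the month-24 result simply returns the share put in, so no particular number of points should be attributed to this study. Nor is every affected patient a 24-month survivor: one who withdraws is censored at the last visit, and one whose stop is later recorded becomes an event. If unresumed pauses are rare, the effect is small.

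Drug survival is one of eleven secondary endpoints, is reported descriptively, and does not enter the primary model. The change is still worth making because the error is one-sided and cheap to remove.

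**What to change.** In SAP 7.1.2.10:

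1. Keep resumed pauses as not terminated.
2. Where no stop is recorded, set status 1 with time = pause start − initiation if tofacitinib is not resumed by the last documented visit, or if another tsDMARD or bDMARD is started during the pause. The second condition is a safeguard for switches that lack the expected stop date.
3. Add two sensitivity runs: one that censors patients with an unresumed pause at pause start, and one that counts every pause as a stop. The second is a lower bound, not a better estimate.
4. State one analysis set for drug survival and make SAP 9.2.3.10 and the table in 9.2.6 agree. Say also whether the on-drug data restriction in 9.2.3 applies to this endpoint.

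The cost is a few sentences of SAP wording and two extra Kaplan-Meier runs, using the stop and pause entries that the SAP already draws on. Reported drug survival becomes slightly less favourable, and some pauses still open at the last visit will count as stops although they might have been resumed. This is a counting rule for the analysis and has no bearing on how patients are treated.
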